## **6.7 Multicentre Studies**

As stated in the CSP, none of the analyses will be adjusted by study center.

## **6.8 Examination of Subgroups**

NA

## **6.9 Interim Analysis**

No formal Interim Analysis is foreseen for this study.

## **6.10 Reporting Conventions**

P-values  $\geq 0.0001$  will be reported to four (4) decimal places; p-values less than 0.0001 will be reported as  $<0.0001$ . The mean and median will be displayed to one decimal place greater than the original value and the measure of variability (e.g., standard deviation) will be displayed to two decimal places greater than the original value.

## 8 LIST OF OUTPUT

### 8.1 Tables to be produced for the Clinical Study Report (Section 14 according to ICH E3)

Demographic data and baseline characteristics will be showed stratifying by treatment group (IMP and placebo) and overall.

Efficacy and safety analysis tables will be showed stratifying by treatment group, as well as each timepoint, as applicable.

For continuous variables, summary statistics will be included in the MMRM tables.

#### 14.1 DEMOGRAPHIC DATA

##### Patient disposition

Table	Title	Pop	Top.Line
14.1.1	Patient disposition: Number of patients in each analysis set and reason for exclusion	ALL	X
14.1.2	Number of patients by visit	ALL	
14.1.3	Reason for finish the study prematurely	ALL	

##### Demographic and baseline characteristics

Table	Title	Pop	Top.Line
14.1.4	Demographics	SAF	
14.1.5	Urine pregnancy test	SAF	
14.1.6	Cataract diagnosis	SAF	
14.1.7	Relevant Medical History	SAF	

#### 14.2 EFFICACY DATA

##### Primary efficacy analysis

Table	Title	Pop	Top.Line
14.2.1.1	Percentage of patients with anterior chamber cell grade of "0" compared to placebo at Day 8	FAS	X
14.2.1.2	Percentage of patients with anterior chamber cell grade of "0" compared to placebo at Day 8	PP at Visit 3	

### **Main Secondary efficacy analysis**

Table	Title	Pop	Top.Line
14.2.2.1	Proportion of patients with VAS pain score of "0" (no eye pain) compared to placebo at Day 8.	FAS	X
14.2.2.2	Proportion of patients with VAS pain score of "0" (no eye pain) compared to placebo at Day 8.	PP at visit 3	

### **Secondary efficacy analysis**

Table	Title	Pop	Top.Line
14.2.3.	Proportion of patients with anterior chamber cell grade of "0" compared to placebo at Day 3, Day 15 and Day 29	FAS	X
14.2.4.1	Change from Baseline to Day 3, Day 8, Day 15 and Day 29 compared to placebo in the proportion of patients with different anterior chamber cell grades. Improvement and no Improvement table.	FAS	
14.2.4.2	Change from Baseline to Day 3, Day 8, Day 15 and Day 29 compared to placebo in the proportion of patients with different anterior chamber cell grades. Descriptive table	FAS	
14.2.5.1	Change from Baseline to Day 3, Day 8, Day 15 and Day 29 compared to placebo in the proportion of patients with different anterior chamber flare grades. Improvement and no Improvement table.	FAS	
14.2.5.2	Change from Baseline to Day 3, Day 8, Day 15 and Day 29 compared to placebo in the proportion of patients with different anterior chamber flare grades. Descriptive table	FAS	
14.2.6.	Proportion of patients with anterior chamber cell grade of " $\leq 0.5+$ " and flare grade of "0" compared to placebo at Day 3, Day 8, Day 15 and Day 29.	FAS	
14.2.7.	Proportion of patients with anterior chamber cell grade of " $\leq 1+$ " compared to placebo at Day 3, Day 8, Day 15 and Day 29.	FAS	
14.2.8.	Proportion of patients with anterior chamber cell grade of "0" and flare grade of "0" compared to placebo at Day 3, Day 8, Day 15 and Day 29.	FAS	
14.2.9.1	Frequency of chemosis (yes/no) compared to placebo at Baseline, Day 3, Day 8, Day 15 and Day 29.	FAS	

14.2.9.2	Frequency of bulbar conjunctival injection (yes/no) compared to placebo at Baseline, Day 3, Day 8, Day 15 and Day 29.	FAS	
14.2.9.3	Frequency of ciliary injection (yes/no) compared to placebo at Baseline, Day 3, Day 8, Day 15 and Day 29.	FAS	
14.2.9.4	Frequency of corneal edema (yes/no) compared to placebo at Baseline, Day 3, Day 8, Day 15 and Day 29.	FAS	
14.2.9.5	Frequency of keratic precipitates (yes/no) compared to placebo at Baseline, Day 3, Day 8, Day 15 and Day 29.	FAS	
14.2.10.1	Change from Baseline to Day 3, Day 8, Day 15 and Day 29 compared to placebo in the proportion of patients with chemosis (yes/no)	FAS	
14.2.10.2	Change from Baseline to Day 3, Day 8, Day 15 and Day 29 compared to placebo in the proportion of patients with bulbar conjunctival injection (yes/no)	FAS	
14.2.10.3	Change from Baseline to Day 3, Day 8, Day 15 and Day 29 compared to placebo in the proportion of patients with ciliary injection (yes/no)	FAS	
14.2.10.4	Change from Baseline to Day 3, Day 8, Day 15 and Day 29 compared to placebo in the proportion of patients with corneal edema (yes/no)	FAS	
14.2.10.5	Change from Baseline to Day 3, Day 8, Day 15 and Day 29 compared to placebo in the proportion of patients with keratic precipitates (yes/no)	FAS	
14.2.11.1	Change from Baseline to Day 3, Day 8, Day 15 and Day 29 compared to placebo in the severity of chemosis. Improvement or no Improvement.	FAS	
14.2.11.2	Change from Baseline to Day 3, Day 8, Day 15 and Day 29 compared to placebo in the severity of chemosis. Descriptive table	FAS	
14.2.11.3	Change from Baseline to Day 3, Day 8, Day 15 and Day 29 compared to placebo in the severity of bulbar conjunctival injection. Improvement or no Improvement.	FAS	
14.2.11.4	Change from Baseline to Day 3, Day 8, Day 15 and Day 29 compared to placebo in the severity of bulbar conjunctival injection. Descriptive table	FAS	
14.2.11.5	Change from Baseline to Day 3, Day 8, Day 15 and Day 29 compared to placebo in the severity of ciliary injection. Improvement or no Improvement	FAS	
14.2.11.6	Change from Baseline to Day 3, Day 8, Day 15 and Day 29 compared to placebo in the severity of ciliary injection. Descriptive table	FAS	
14.2.11.7	Change from Baseline to Day 3, Day 8, Day 15 and Day 29 compared to placebo in the severity of corneal edema. Improvement or no Improvement.	FAS	

14.2.11.8	Change from Baseline to Day 3, Day 8, Day 15 and Day 29 compared to placebo in the severity of corneal edema. Descriptive table	FAS	
14.2.11.9	Change from Baseline to Day 3, Day 8, Day 15 and Day 29 compared to placebo in the severity of keratic precipitates. Improvement or no Improvement	FAS	
14.2.11.10	Change from Baseline to Day 3, Day 8, Day 15 and Day 29 compared to placebo in the severity of keratic precipitates. Descriptive table	FAS	
14.2.12	MMRM. Change from Baseline to Day 3, Day 8, Day 15 and Day 29 compared to placebo in the visual analog scale (VAS) photophobia score.	FAS	
14.2.13	MMRM. Change from Baseline to Day 8, Day 15 and Day 29 compared to placebo in Snellen best.corrected visual acuity (BCVA) score.	FAS	
14.2.14	MMRM. Change from Baseline to Day 3, Day 8, Day 15 and Day 29 compared to placebo in the VAS pain score.	FAS	X
14.2.15	Proportion of patients with VAS pain of "0" compared to placebo at Day 3, Day 15 and Day 29.	FAS	X
14.2.16.1	Change from baseline to Day 3, Day 8, Day 15 and Day 29 compared to placebo in the proportion of patients with different discomfort grades. Improvement or no Improvement	FAS	
14.2.16.2	Change from baseline to Day 3, Day 8, Day 15 and Day 29 compared to placebo in the proportion of patients with different discomfort grades. Descriptpve table	FAS	
14.2.17.1	Proportion of patients with no discomfort ("None") compared to placebo at Day 3, Day 8, Day 15 and Day 29.	FAS	
14.2.17.2	Eye discomfort by visit and treatment. Descriptive statistics	FAS	
14.2.18	MMRM. Change over time in the VAS pain score reported in the patients' diaries compared to placebo.	FAS	X
14.2.19	Percentage of patients with anterior chamber cell grade of "0" compared to placebo at Day 8. Sensitivity Analysis	FAS	

### 14.3 SAFETY DATA

#### Adverse events

Table	Title	Pop	Top.Line
14.3.1.1	Summary of Treatment Emergent Adverse Events (TEAEs)	SAF	X
14.3.1.2	Treatment Emergent Adverse Events by System Organ Class and Preferred Term	SAF	

14.3.1.3	TEAEs by SOC and PT by worst severity	SAF	
14.3.1.4	TEAEs by SOC and PT by worst relationship	SAF	
14.3.1.5	TEAEs related to IMP/Placebo	SAF	
14.3.1.6	TEAEs leading to discontinuation	SAF	
14.3.1.7	Serious TEAEs	SAF	
14.3.1.8	Serious TEAEs related to IMP/Placebo	SAF	
14.3.1.9	TEAEs AESI	SAF	
14.3.1.10	TEAEs AESI related to IMP/Placebo	SAF	
14.3.2	Listings of Deaths Other Serious Adverse Events, and Other Significant Adverse Events	SAF	

14.3.3 [This title is reserved for narratives.]

### **Other Safety assessments**

Table	Title	Pop	Top.Line
14.3.4.1	Absolute and Percentage change from Baseline in Vital Signs by treatment regimen. Descriptive Statistics	SAF	
14.3.4.2	Summary statistics. Change from Baseline to Day 3, Day 8, Day 15 and Day 29 compared to placebo in intraocular pressure (IOP).	SAF	X

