**Table 1 Schedule of Observations**

Visit number	Visit -1 Screening	Cataract Surgery	Visit 1 Baseline	Visit 2	Visit 3	Visit 4	Visit 5	Early termination
Study time-point	Day -7 (± 3 days)	Day -1	Day 1	Day 3 (+ 1 day)	Day 8 (± 1 day)	Day 15 (± 2 days)	Day 29 (± 2 days)	
Eligibility criteria	X		X					
Dated and signed Informed consent for study participation 	X							
Demographic data	X							
Relevant medical history 	X		X					
Prior medications 	X		X					
Urine pregnancy test	X		X					
Eye pain (VAS) 	X		X	X	X	X	X	X
Eye discomfort 	X		X	X	X	X	X	X
Photophobia (VAS) 	X		X	X	X	X	X	X
Vital signs examination 			X	X	X	X	X	X
Physical and eye examination	X							X
Slit-lamp examination	X		X	X	X	X	X	X
Intraocular pressure	X		X	X	X	X	X	X
Best-corrected visual acuity Snellen	X		X		X	X	X	X
Indirect ophthalmoscopy	X		X			X	X	X
Randomization			X					
Dispensation of IMP			X					
Administration of first IMP dose			X					
Distribution of patient diary			X					
Review of patient diary				X	X	X		X 
Return of patient diary						X		X 

Return of remaining IMP						X		X 
Adverse events 	X		X	X	X	X	X	X
Concomitant medications			X	X	X	X	X	X
End of study							X	X

Abbreviations: IMP, investigational medicinal product; VAS, visual analog scale.

All ocular assessments must be performed in both eyes.

1. Informed consent must be signed and dated prior to any study-related procedure and before any data is recorded in the case report form
2. Relevant medical history will include any previously diagnosed ophthalmic abnormalities and ocular surgeries (including laser procedures). Relevant medical history at Visit 1 (Day 1) will cover the time from the Visit -1 (Screening).
3. Medications taken 2 months prior to Visit -1 (prior 36 months for ocular implants and/or intravitreal injections)
4. VAS scales and discomfort should be assessed prior to any physical evaluation
5. Vital signs assessments to be completed 15 min before any ocular assessment. Additionally, baseline Vital signs on Visit 1 to be completed at least  $30 \pm 10$  min before IMP administration.
6. If occurred within the 14 days planned for the treatment period.
7. Expected changes or the presence of inflammation or pain resulting from routine cataract surgery will not be captured as adverse events.

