- 16) Presence of Fuchs' endothelial dystrophy (loss of endothelial cells that may result in chronic corneal edema after cataract surgery especially if high energy was used during phacoemulsification)
- 17) Presence of *cornea guttata*
- 18) Pupil dilation lower than 4.5 mm
- 19) Presence of lower lacrimal duct obstruction and/or history of infectious dacryocystitis
- 20) Presence of IOP  $\geq 24$  mmHg in the study eye at Visit 1
- 21) Participation in any study of an investigational topical or systemic new drug or device within 30 days prior to the Screening visit (Visit -1), or at any time during the study
- 22) Prior participation in the study described in this protocol, unless patient was not randomized
- 23) In the opinion of the investigator or study coordinator, be unwilling or unable to comply with study protocol or unable to successfully instill eye drops
- 24) Disease, condition (including monocular patients), or disorder that in the judgement of Investigator could confound study assessments or limit compliance to study protocol

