### **8.3.10 Precautions/Overdose**

The risk of overdosing in general in this study is considered to be very low. The planned maximum exposure will be approximately 0.066 mg/day of clobetasol propionate (approximately 0.924 mg of clobetasol propionate over a period of 14 days). The total amount of clobetasol propionate administered in the toxicological pre-clinical study (at the highest dose) was 4 times above the clinical trial dose, exhibiting no ocular toxicity. Systemic HED in pre-clinical study was 17-times higher compared to dosing in one eye of adults.

An expected AR that could represent a severe condition is the induction of IOP rise (and associated ocular pain and redness). In case of IOP >30mmHg, the investigator discretion is advised, using preferred standard of care at the study site. The use of specific ocular hypotensor eye drops (like beta blockers / alpha agonists / carbonic anhydrase inhibitors) is recommended.

Nevertheless, unintentional administration of any dose that deviates from the scheduled regimen will be documented and reported by center personnel.

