## 9. STATISTICAL METHODS

### 9.1 General Statistical Methods

In general, data will be summarized by means of summary statistics. Continuous data will be presented with the number of observations, mean value, confidence intervals, standard deviation, minimum, Q1, median, Q3 and maximum value. Change from baseline to each post-baseline visit will be also described using descriptive statistics. Categorical data will be presented as counts and percentages.

The data will be presented for each treatment group by visit.

Individual patient data will be listed for all enrolled patients. Listings will be sorted by center and patient number and labelled by randomized treatment group.

Before unmasking the study data, a separate statistical analysis plan (SAP), which will provide the technical details of the statistical analysis outlined below, will be prepared and approved.

For statistical analyses, the following definitions will be applied:

- Baseline: Baseline is defined as Visit 1 (Day 1, 24 h after the cataract surgery).
- Randomized treatment group: The treatment that was assigned at the time of randomization.

The assessments performed at Visit 1 (Day 1) will be considered the baseline values.

All data collected during study follow-up will be displayed and analyzed according to the actual visit data in the eCRF.

Unless otherwise stated, all statistical tests will be conducted using two-sided alpha = 0.05.

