## 6.3 Hypotheses and Statistical Methods

### 6.3.1 Definitions

Baseline	( Visit 1 (Day 1, 24 h after the cataract surgery).
Time calculation	Differences between dates to express duration will be calculated as the final date - initial date + 1. To convert these days differences to other units, the following conversion factors will be used: 1 year = 365.25 days and 1 month = 30.4375 days.  Ex. Age = (informed consent date – date of birth + 1) / 365.25
Absolute change from Baseline	Absolute change from Baseline at Visit X will be calculated as:  Absolute change from Baseline = Visit X - Baseline
Percentage change from Baseline	Percentage change from Baseline at Visit X will be calculated as:  Percentage change from Baseline [%] = ((Visit X - Baseline)/Baseline) *100  In case of Baseline = 0 no percentage change from baseline will be calculated.
Signs of ocular inflammation (yes/no)	The presence/absence of the different signs of ocular inflammation: Chemosis, Bulbar conjunctival injection, ciliary injection, corneal edema, keratic precipitates will be defined as:  No: grade=0 (absence)  Yes: grade=1, 2 or 3 (presence)
Conversion Snellen to LogMar	Step 1. Mar = Snellen Denominator/Snellen Numerator  Step 2. LogMar = log (Mar)  Example: Snellen 20/40  Mar = 40/20 = 2  LogMar= log(2) = 0.3
Treatment Emergent Adverse Event	Treatment Emergent Adverse Events (TEAEs) are defined as an event that emerges during treatment  having been absent pre-treatment or worsens relative to the pre-treatment state:  First dose IMP/Pacebo date ≤ start date AE ≤ last dose IMP/Placebo date
Rescue medication	The following prohibited medications will be considered as rescue medication when administered to subjects not responding to IMP or placebo: 

▪ Any systemic or local therapy with corticosteroids (other than the study drug) or immunosuppressant (except pre-surgical and/or surgical administration of 1 drop of a topical NSAID or corticosteroid, at the investigator discretion)

▪ Any topical ocular medication (except preservative-free antibiotics for prophylactic purposes and preservative-free artificial tears)

	

▪ Any systemic NSAID or opioids drugs (except occasional use of OTC formulations titrated no more than one single dose per week)

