### **6.3.2 Summary Statistics**

Data will be summarised by means of summary statistics. For continuous data the following summary statistics will be presented: number of observations, mean, standard deviation (SD), minimum, Q1, median, Q3 and maximum. 95% CI of the mean will also be presented for efficacy and safety data. Change from baseline to each post-baseline visit will be also described using descriptive statistics. Categorical data will be presented as counts and percentages.

Summary statistics will be presented by treatment group and visit, as applicable.

Certain presentations (withdrawals, patient exclusion from datasets, baseline and background characteristics and primary efficacy data) may be broken down by study center, if relevant.

All data collected during study follow-up will be displayed and analyzed according to the actual visit data in the eCRF.

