### 6.3.10 Adverse Events

AEs data are collected on the 'Adverse Events' eCRF form.

AEs will be coded according to the Medical Dictionary for Regulatory Activities (MedDRA) system, the latest version and tabulated by System Organ Class (SOC) and by Preferred Term (PT).

A Treatment-Emergent Adverse Event (TEAE) is defined as an AE observed after starting administration of IMP or placebo (see Section 6.3.1).

TEAEs will be summarized by presenting, for each treatment regimen, the number of events and the number and percentage of patients with:

- Any TEAE
- Any Serious Treatment Emergent Adverse Event (STEAE)
- Any TEAE of Special Interest (TEAESI)
- Any TEAE related to IMP/Placebo
- Any TEAE leading to treatment discontinuation (drug withdrawn)
- Any STEAE related to IMP/Placebo
- Any TEAESI related to IMP/Placebo

The number and percentage of TEAEs by causality and the number and percentage of mild moderate and severe TEAEs will be tabulated by SOC, PT and treatment arm. All tables with TEAEs by SOC and PT stratified by treatment regimen will only be counted by patient once within each PT.

The following tables will be provided with TEAEs by SOC and PT stratified by treatment regimen: TEAEs, TEAEs related to IMP/Placebo, TEAEs leading to discontinuation, STEAEs, STEAEs related to IMP/Placebo, TEAESI and TEAESIs related to IMP/Placebo.

TEAEs, STEAEs and TEAESIs will be tabulated by severity (mild, moderate or severe) and relationship to treatment (No: not related, unlikely related, Yes: possible, probable and certain). If a patient has more than one event with the same PT, the AE will only be counted once and the worst/maximal severity and the worst/strongest relationship will be used.

A listing of all AEs will be presented, whether treatment emergent or not. TEAEs will be flagged in this listing. A separate listing for deaths, STEAEs, AESIs and TEAEs leading to discontinuation will be provided (if any).

The following AEs (SOC, PT) of special interest (AESI) will be evaluated by Investigators at all study visits and time points (as applicable):

- IOP rise over 30 mmHg (SOC- INVESTIGATIONS, PT-INTRAOCULAR PRESSURE INCREASED)
- Pain/discomfort associated with IMP instillation (SOC-EYE DISORDERS, PT-EYE PAIN, OCULAR DISCOMFORT and related with IMP)

SAF will be used for all AE related summaries.

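### Measured IOP is tabulated only as summary statistics of change from Visit 1; no table counts, by arm, the patients with a marked rise, and the AESI tables only partly fill the gap.

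*SAP*

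**What the plan says.** **Endpoint and baseline.** Change in IOP from baseline to Days 3, 8, 15 and 29 against placebo is a safety endpoint (protocol 7.4, SAP 3.3). In protocol 9.1, "Baseline is defined as Visit 1 (Day 1, 24 h after the cataract surgery"); SAP 6.3.1 agrees: "Visit 1 (Day 1, 24 h after the cataract surgery"). The "Intraocular pressure" row of protocol Table 1 is marked at Visit -1, before surgery, and at Visits 1 to 5. No analysis uses the Visit -1 value. Exclusion 20 removes patients with a pressure of 24 or more "mmHg in the study eye at Visit 1".

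**Tables.** SAP 14.3.4.2 (safety set, flagged for top-line reporting) is "Summary statistics. Change from Baseline to Day 3, Day 8, Day 15 and Day 29 compared to placebo in intraocular pressure (IOP"). For continuous data, SAP 6.3.2 defines this as "number of observations, mean, standard deviation (SD), minimum, Q1, median, Q3 and maximum", with a 95% CI of the mean for safety data. SAP 6.3.11 has no text on IOP. Protocol 9.1.13.1 has none either, and its shift tables are for vital signs.

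**Adverse events.** Protocol 8.3.10 states: "An expected AR that could represent a severe condition is the induction of IOP rise (and associated ocular pain and redness"). SAP 6.3.10 lists as an AESI "IOP rise over 30 mmHg (SOC- INVESTIGATIONS, PT-INTRAOCULAR PRESSURE INCREASED"). Tables 14.3.1.9 and 14.3.1.10 present AESIs by arm, restricted to treatment-emergent events. SAP 6.3.1 ends the treatment-emergent window on the date of the last dose. Listing 16.2.11 gives every IOP value.

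**The concern.** A steroid pressure response is usefully described by how many patients had it and how large it was. A mean change dilutes a large rise in a few patients, and the plan has no count of measured rises to set beside it. The one categorical criterion, the AESI, works through adverse event reporting. It therefore depends on a level or change tied to 30 mmHg, on the investigator's decision to report, and on an onset date within dosing. At stake is how precisely the trial can describe its main expected drug risk, by arm and through the Day 29 follow-up that the safety endpoints promise. The validity of the efficacy result is not affected.

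**Working it through.** **1. Figures in the plan.** The documents give no power or precision for IOP. The arm sizes of 140 and 70 come from the primary endpoint (22% against 7%, two-sided 0.05, 80% power). That calculation reproduces: the pooled chi-square formula gives 204 against the stated 202, power at 202 is 80.2%, and 202/0.96 = 210.4 against the stated 210. It has no bearing on IOP beyond fixing the arm sizes.

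**2. What the AESI tables count.** Three conditions must all hold.
- *Size.* A rise from 15 to 30 mmHg (+15) or from 14 to 27 mmHg (+13) does not exceed 30 mmHg. It reaches a table only if the investigator reports it as an adverse event.
- *Reporting.* Note 7 to protocol Table 1 keeps expected changes from routine surgery out of the adverse event record, so some judgement is built in.
- *Timing.* Dosing lasts 14 days from Day 1. Visit 4 falls on Days 13 to 17, so an elevation first found there may be dated after the last dose. Visit 5 falls on Days 27 to 31, so one first found there always is.

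**3. Dilution in the mean.** All inputs except the arm sizes are assumptions: a share r of active patients rises by 12 mmHg, and the SD of change is 3 to 4 mmHg otherwise.
- Mean shift = 12r.
- Active-arm variance = SD² + r(1 − r) × 12².
- SE of the difference = √(active-arm variance/140 + SD²/70).

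At r = 5%, 7 of 140 patients rise and the mean shift is 0.60 mmHg. The added variance is 0.05 × 0.95 × 144 = 6.84.
- SD 3: SE = √(15.84/140 + 9/70) = 0.49.
- SD 4: SE = √(22.84/140 + 16/70) = 0.63.

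The shift is therefore about 1.0 to 1.2 SE, inside a 95% half-width of 0.96 to 1.23 mmHg. The range over r:

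| r | patients of 140 | mean shift (mmHg) | SE, SD 3 to 4 | shift/SE |
|---|---|---|---|---|
| 3% | 4 | 0.36 | 0.47 to 0.61 | 0.6 to 0.8 |
| 5% | 7 | 0.60 | 0.49 to 0.63 | 1.0 to 1.2 |
| 10% | 14 | 1.20 | 0.53 to 0.66 | 1.8 to 2.3 |

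Safety is compared descriptively, so the SE serves only as a yardstick for what a reader can see in the table.

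**4. What the other summary statistics show.** At 5%, the active-arm SD grows from 3 to √15.84 = 3.98, or from 4 to √22.84 = 4.78. In a simulation with a 10 mmHg rise, SD 4 and 5% affected, the expected maximum among 140 patients moved from 10.5 to 15.3 mmHg, and Q3 only from 2.7 to 3.2. These figures suggest a tail but do not say how many patients are in it.

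**5. What a count would show.** With normal variation, r = 5%, a 12 mmHg rise and a cut-off of 10 mmHg, the probability of being counted in the active arm at one visit is 0.05 × Φ(2/SD) + 0.95 × Φ(−10/SD).
- SD 4: 0.05 × 0.691 + 0.95 × 0.006 = 0.040, or 5.7 of 140, against 0.4 of 70 on placebo.
- SD 3: 0.038, or 5.3 of 140, against 0.03 of 70.

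The count does not recover all 7 patients, but it makes the pattern plain.

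**6. The reference visit.** Take an eye at 14 mmHg at Visit -1, 22 at Visit 1 and 25 at Day 15. It reads +3 from Visit 1 and +11 from Visit -1. The 8 mmHg between the two references arose before any study drug. Each figure answers a different question, and only the change from Visit 1 isolates the period on treatment.

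**The case against.** The strongest reply is that large rises are visible already. Rises over 30 mmHg are an AESI, assessed at every visit, reported to the sponsor within 24 hours and tabulated by arm. IOP events below that level, if reported, appear by preferred term. The summary includes SD, Q3 and maximum; every value is listed; and pressure-lowering drops would appear among concomitant medications. This stands, and it rules out saying that the signal is hidden or that the trial would report none. What remains is that none of these outputs counts measured rises by arm: listings must be counted by hand, and the tables depend on reporting.

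On timing, SAP 6.3.10 words the treatment-emergent definition without an end date, and protocol 9.1.13 mentions tabulating all adverse events. But SAP 6.3.10 refers back to 6.3.1, which closes the window, and every adverse event table in the SAP output list (14.3.1.1 to 14.3.1.10) is treatment-emergent.

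A reader might also infer that the Visit 1 baseline is wrong because surgery has raised the pressure by then. The documents do not support this. Exclusions 13 and 20 remove high values but do not say that eligible eyes are raised at 24 hours, and exclusion 20 caps Visit 1 below 24 mmHg. Visit 1 is the last value before dosing, and patients are randomized there, so any surgical effect is equal in expectation in both arms and the between-arm difference is unbiased.

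Finally, a 10 mmHg cut-off appears nowhere in the documents. That is fair: it is an example of a reporting threshold, and the sponsor should choose and justify its own.

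**Conclusion.** The gap is real but limited. Measured IOP has no by-arm count of marked rises, and the AESI tables miss two groups: rises that end at or below 30 mmHg and are not reported, and elevations first found after the last dose. Under the assumed 5% share, 12 mmHg rise and SD of 3 to 4, seven affected patients move the mean by 0.6 mmHg, about one SE; over 3 to 10% the shift is 0.4 to 1.2 mmHg. At the upper end the mean itself would begin to show it. None of these inputs is in the documents, and the size scales with them. The Visit 1 reference should stay. This is a change that should be made; it is not a flaw that undermines the trial.

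**What to change.** - Keep 14.3.4.2 with Visit 1 as the reference.
- Add one descriptive table on the safety set giving, by arm, at each visit and at any post-dose visit through Day 29, the number and percentage of study eyes with a prespecified rise from Visit 1 (for example 10 mmHg or more) and above prespecified absolute levels, with a 95% CI for the difference. These are reporting thresholds only and change nothing in patient care.
- Repeat the change and the count from Visit -1 as supportive only, and say in the SAP that this change mixes surgical and drug effects.
- Reconcile the AESI wording in protocol 8.3.9 and SAP 6.3.10, which can be read as a change of more than 30 mmHg, with protocol 8.3.10, which refers to a level above 30 mmHg.

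The cost is a few lines of SAP text and one table with a supportive repeat, before unmasking. All the values are already collected.
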